| | 7.7 | | MENTS | |
| | 7.7 | 7.1 | Treatment Compliance and Extent of Exposure | |
| | | 7.2 | Prior and Concomitant Medications | |
| | 7.8 | EFFIC | ACY ANALYSES | - |
| | | 8.1 | Primary Efficacy Analysis | |
| | | 8.2 | Sensitivity Analyses | |
| | | 8.3 | Supplementary Analysis | |
| | 7.8 | 8.4 | Analysis Based on Adjustment of Covariates | |
| | | 8.5 | Examination of Subgroups | |
| | | 8.6 | Analysis of Secondary Efficacy Endpoints | |
| | | | Y ANALYSES | |
| | 7.9 | 9.1 | Adverse Events | |
| | | 9.2 | Laboratory Test | |
| | 7.9 | 9.3 | Vital Signs, Height, Weight, and BMI | |
| | | 9.4 | 12-Lead ECG | |
| | 7.9 | 9.5 | Columbia Suicide Severity Rating Scale (C-SSRS) | |
| | 7.9 | 9.6 | Infrequent Behaviors Checklist | |
| | 7.9 | 9.7 | Other Special Tests | 38 |
| 8 | VA | ALIDA | TION | 39 |
| 9 | RE | FERE | NCES | 39 |
| АР | PEN | DIX 1. | EXCLUSION CRITERIA FOR THE PER PROTOCOL POPULATIONS | 41 |
| AP | PEN | DIX 2. | LIST OF TABLES, LISTINGS, AND FIGURES | 42 |

LIST OF ABBREVIATIONS

| AE | Adverse event |
|--------|--|
| AESI | Adverse event of Special Interest |
| BID | Bis in die, twice daily |
| CRO | Contract Research Organization |
| CRF | Case report form |
| ECG | Electrocardiogram |
| FDA | Food and Drug Administration |
| GCP | Good Clinical Practice |
| IA | Impulsive Aggression |
| ICF | Informed Consent Form |
| ICH | International Conference on Harmonisation |
| IND | Investigational New Drug Application |
| ITT | Intent-to-Treat |
| IV | Intravenous |
| IWRS | Interactive web-based randomization system |
| kg | kilogram |
| mcg | Microgram |
| MedDRA | Medical Dictionary for Regulatory Activities |
| mg | Milligram |
| msec | Millisecond |
| РК | Pharmacokinetic(s) |
| PO | Oral |
| PP | Per Protocol |
| PT | Preferred term in MedDRA and WHODD |
| SAE | Serious adverse event |
| SAP | Statistical analysis plan |
| SD | Standard deviation |
| SM | Study Medication |
| SOC | System Organ Class in MedDRA |
| TDD | Total Daily Dose |
| TEAE | Treatment-emergent adverse event |
| TESAE | Treatment-emergent serious adverse event |
| WHODD | WHO Drug Dictionary |

REVISION HISTORY

This is Version 2.1 of the Statistical Analysis Plan (SAP).

Summary of changes to the SAP from Version 2 submitted to FDA on 17Dec2019.

| Section | Page | Description of Change | Rationale |
|---------|------|---|--|
| 7.1.2 | 25 | The modified ITT is defined to exclude subjects with baseline IA frequency <6 per week | Retrospective Modified Overt Aggression Scale (R-MOAS) score was used for inclusion criteria but the primary analysis was analyzed based on data collected using IA diary Instrument. Based on discussion with KOLs, subjects with baseline IA frequency <6 per week for primary endpoint are considered to be normative. The original definition of the primary efficacy analysis population is modified based on advise from KOLs to detect treatment difference. This population will be called mITT and will be used for the primary analysis. |
| 7.1.3 | 25 | The ITT population is moved to Section 7.1.3 The first paragraph and the first sentence of 2 nd | Per FDA advise to submit results under the original definition of the primary efficacy analysis population |
| 7.8.1 | 29 | paragraph re-phrased | Clarification |
| 7.8.2 | | | Clarification |
| 7.0.6 | 22 | Subsection 7.8.6.1 and 7.8.6.2 for key secondary analysis and additional | Clasification |
| 7.8.6 | 33 | secondary analysis created. | Clarification |

1 INTRODUCTION

The purpose of this statistical analysis plan (SAP) is to ensure the credibility of the study findings by specifying the statistical approaches to the analysis of the data prior to database lock. This SAP covers the planned analyses of all data collected on the eCRFs and diary pages, and will identify handling of data issues. The statistical analysis plan presented in this document will supersede the statistical analysis methods described in the clinical protocol. Any deviations/changes from the planned analyses described in this SAP will be identified, with justification, in the appropriate section of the clinical study report. This SAP is based on the clinical study protocol 810P302, version 7.0, dated 29 March 2019 and its associated electronic case report forms (eCRF).

2 STUDY OBJECTIVES

2.1 Primary Objective

The primary objective is to assess the efficacy and safety of SPN-810 in reducing the frequency of impulsive aggression (IA) behaviors in pediatric patients with attention-deficit/hyperactivity disorder (ADHD) when taken in conjunction with standard ADHD treatment.

2.2 Secondary Objectives

2.2.1 Key Secondary Objective

The key secondary objective of the study is to assess the effect of SPN-810 on the Clinical Global Impression – Severity Scale (CGI-S).

2.2.2 Secondary Objective

The secondary objectives of the study are to assess the following:

- The effect of SPN-810 on the Investigator-rated Clinical Global Impression Improvement Scale (CGI-I)
- The effect of SPN-810 on the child's overall health as measured by the Child Health Questionnaire Parent Form 28-item (CHQ-PF28)
- The effect of treating the child with SPN-810 on the parent-child relationship as measured by the Parenting Stress Index Short Form version 4 (PSI-4-SF)
- The effect of SPN-810 on the caregiver-completed CGI-I
- The effect of SPN-810 on inattention, hyperactivity-impulsivity and oppositional defiant disorder measured by the SNAP-IV Rating Scale
- The effect of SPN-810 on the responder rate (defined as ≥ 50 % in the reduction of the frequency of IA behaviors)
- The effect of SPN-810 on the responder rate (defined as ≥ 30 % in the reduction of the frequency of IA behaviors)

2.3 Tertiary Objectives

3 STUDY DESIGN

3.1 General Description

Protocol 810P302 is a randomized, placebo-controlled, double blind, multicenter, parallel group, fixed dose study to demonstrate the efficacy, safety, and tolerability of SPN-810 in the treatment of IA in patients aged 6-12 years with ADHD in conjunction with standard ADHD treatment. The study design is presented schematically in Figure 1 and Figure 2. The study is divided into three phases: Pre-Treatment, Treatment, and Conversion/Taper.

Figure 1: Treatment Schedule (Conversion)

[figure not shown]
[figure not shown]

Figure 2: Treatment Schedule (Taper)

Following screening, eligible subjects will enter a flexible 15-day baseline period, at which time the IA diary will be issued to the subject's primary caregiver. At the end of the baseline period, eligible subjects whose primary caregiver has maintained at least 80% compliance with the IA diary will be randomized. Per the original randomization eligible subjects who complete the baseline period and meet the requirements for the double-blind study will be randomized at Visit 3 (Day 1) in a 1:1:1 ratio to receive 18 mg/day, 36 mg/day SPN-810 or placebo and proceed to the titration period, which will be two weeks. However, based on the 810P301 study Interim Analysis result decision, the 18 mg arm was dropped partway through the study. As a result, subjects planned to be randomized to the 18 mg arm were be re-allocated to the 36 mg or placebo arm in a ratio of 2:1.

Subjects will be titrated to maintenance dose over a period of 2 weeks. Following dose titration, subjects on active treatment will be maintained at their designated dose level for 3 weeks.

3.2 Schedule of Visits and Procedures

All subjects who are randomized and take any study medication (SM) will be followed according to the protocol regardless of the number of doses of SM taken, unless consent for follow-up is withdrawn. Table 1 below presents the schedule of visits and procedures for the study.

Table 1: Schedule of Visits and Procedures

| Phase | Pre-treatment | | Treatment | | | | Conversion/ |
|--|---------------|------------|------------------|----------------|----------------|-------------|-------------|
| Period | Screening | Baseline | ٦ | litration | Mainte | nance | Taper |
| VISIT NUMBER | 1 | 2 | 3 | 4 | 5 | 6 | 7 |
| DAY | -45 | -15 | 1 | 8 | 15 | 36 | 43 |
| WINDOW (DAYS) | ≤45d prior to | ≥15d prior | 0 ^c | 7d±2d from | 14d±2d from | 21d±3d from | 7d±1d from |
| | Visit 3 | to Visit 3 | 0 | Visit 3 | Visit 3 | Visit 5 | Visit 6 |
| Informed Consent/Assent ^a | X b | | | | | | |
| R-MOAS, K-SADS-PL 2013 & Vitiello Aggression | х | | | | | | |
| Scale | ^ | | | | | | |
| Medical History | Х | | X d | | | | |
| Demographics | Х | | | | | | |
| Physical Examination | Х | | | | | Х | |
| ECG (12-lead) | Х | | | Х | | Х | |
| Inclusion/Exclusion Criteria | Х | | | | | | |
| Randomization | | | X ^{b,e} | | | | |
| Urine Drug Screen | Х | | Х | | | | |
| Urine Pregnancy Test ^f | Х | | Х | | | | Х |
| Diary Training & Distribution or Evaluation | | Х | X e | Х | Х | Х | |
| Vital Signs ^g | Х | | | | | | Х |
| Weight, height, BMI | Х | | Х | Х | Х | Х | Х |
| Hematology/chemistry/Urinalysis | Х | | Х | | | Х | Х |
| PK Blood Sampling | | | | X ^h | X ^h | | |
| Columbia Suicide Severity Rating Scale (CSSRS) | Х | | Х | Х | Х | Х | Х |
| Investigator CGI-S | Х | | Х | Х | Х | Х | |
| Caregiver and investigator CGI-I | | | | Х | Х | Х | |

| Phase | Pre-trea | tment | | ٦T | reatment | | Conversion/ |
|---|---------------|------------|----------------|------------|-------------|-------------|-------------|
| Period | Screening | Baseline | Titration | | Maintenance | | Taper |
| VISIT NUMBER | 1 | 2 | 3 | 4 | 5 | 6 | 7 |
| DAY | -45 | -15 | 1 | 8 | 15 | 36 | 43 |
| WINDOW (DAYS) | ≤45d prior to | ≥15d prior | 0 ^c | 7d±2d from | 14d±2d from | 21d±3d from | 7d±1d from |
| | Visit 3 | to Visit 3 | 0° | Visit 3 | Visit 3 | Visit 5 | Visit 6 |
| Efficacy scales (SNAP-IV, CHQ-PF28, PSI-4-SF) | | | Х | | | Х | |
| Safety Scales (Simpson-Angus, Barnes, AIMS) | | | Х | Х | Х | Х | Х |
| Infrequent Behaviors Checklist | | | Х | Х | Х | Х | |
| Adverse Events | | | Х | Х | Х | Х | Х |
| Concomitant Medications | Х | Х | Х | Х | Х | Х | Х |
| Drug Dispensation | | | X b | | Х | Х | |
| Drug Return and Compliance | | | | | Х | Х | Х |
| Diary Return | | | | | | | Х |

^a Written consent must be obtained prior to performing any study-related procedure.

b Access IWRS.

c Visit 3 will occur at least 15 days following Visit 2

d Assess for any clinically significant change in Medical History since screening.

e Diary compliance must be at least 80% (minimum of 12 days out of 15) to qualify for randomization.

f To be performed for female subjects of childbearing potential prior to administration of first dose of SM and will have to be tested as negative for the subject to continue in the study.

g Heart Rate (HR), blood pressure (BP), temperature, and respiratory rate will be measured.

h Total of 5 PK blood samples will be obtained over one or two visits (Visit 4 and/or Visit 5)

3.3 *Study Treatment*

3.3.1 Treatment, Dose, and Mode of Administration

SPN-810 (molindone hydrochloride extended-release tablet) or matching placebo tablets will be administered orally (PO) twice daily (BID). Subjects will be force-titrated over a period of 2 weeks to their final randomized dose at Visit 3. Subjects will be titrated up to the final randomized total daily dose (TDD).

- Treatment 1: placebo
- Treatment 2: 18mg total daily dose (TDD)
- Treatment 3: 36mg TDD

Based on the 810P301 study Interim Analysis result decision, the 18 mg dose arm was dropped partway through the study.

3.3.2 Duration of Treatment and Study Duration

Total subject duration on study is approximately 13 weeks.

- Pre-treatment phase: 45 days
 - Screening period: up to 30 days
 - Baseline period: at least 15 days
- Treatment phase: 5 weeks
 - Titration period: 2 weeks
 - Maintenance period: 3 weeks
- Conversion/Tapering phase: 1 week

3.3.3 Methods of Assigning Subjects to Treatment Group

Allocation of study drug will be completed centrally using an interactive web response system (IWRS) that will determine which kit to assign to the subject. Separate schedules for subject randomization and drug list will be created. The original randomization scheme assigns treatment to each randomization number in a 1:1:1. However, based on the 810P301 study Interim Analysis result decision, the 18 mg arm was dropped partway through the study. As a result, subjects planned to be randomized to the 18 mg arm will be re-allocated to the 36 mg or placebo arm in a ratio of 2:1.

3.3.4 Blinding

Subjects, all site personnel, the Sponsor and its designated Contract Research Organizations (CROs) are blinded with the following exceptions. The CRO and Sponsor personnel who are

involved in the randomization generation, study drug supply, and PK concentration assays are unblinded. However, they are not involved in the routine study monitoring, data cleaning and review, the design of this SAP or data analysis.

3.4 *Hypotheses*

The null and the alternative hypotheses are as in the following.

- H₀: There is no difference between SPN-810 36 mg and placebo in the treatment of IA in subjects with ADHD in conjunction with standard ADHD treatment.
- H_a: There is a difference between SPN-810 36 mg and placebo in the treatment of IA in subjects with ADHD in conjunction with standard ADHD treatment.

3.5 Determination of Sample Size

The original sample size was based on the results from the Phase 2 study. It was assumed that the average treatment difference between SPN-810 dose groups and placebo is 15 with a common standard deviation (SD) =27.3. A sample size of 77 subjects per arm (1:1:1 allocation ratio) would yield 90% power to detect a non-zero difference between the median of 18 mg or 36 mg dose group and the placebo using the Wilcoxon rank-sum test with a 2-sided significance level of alpha=0.05.

After the interim analysis for Study 810P301, the 18 mg dose arm was discontinued for randomization. Subjects planned to be randomized to the 18 mg arm were re-randomized to the 36 mg or placebo arms at a 2:1 allocation ratio. A blinded review of the 810P301 data indicates that the SD for the interim data was actually 34.83 instead of the protocol assumed 27.3. This new SD leads to a total sample size of 306 (adjusted for 20% attrition) subjects. Approximately 167 subjects were randomized prior to the implementation of the 2:1 randomization. It follows that 139 subjects would be randomized in a 2:1 ratio of 36 mg to following the re-calculation of sample size with the new SD.

The sample size was calculated using the nQuery Advisor Software, Version 7.

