## **CLINICAL PROTOCOL SYNOPSIS**

Name of Company:	IND Number: 106,515
Supernus Pharmaceuticals, Inc.	
Name of Product: Molindone Hydrochloride	Name of Active Ingredient:
Extended-Release Tablets (SPN-810)	Molindone Hydrochloride
Protocol Number: 810P302	Phase of Development: 3
and Safety of Molindone Hydrochloride Extended	eficit/Hyperactivity Disorder (ADHD) in Conjunction
Objectives:	
Primary	
The primary objective is to assess the efficacy and impulsive aggression (IA) behaviors in pediatric pa standard ADHD treatment	d safety of SPN-810 in reducing the frequency of atients with ADHD when taken in conjunction with
Secondary The key secondary objective of the study is to ass Impression – Severity Scale (CGI-S).	ess the effect of SPN-810 on the Clinical Global

 
Scale (CGI-I)
 
the effect of SPN-810 on the child's overa Questionnaire Parent Form 28-item (CHQ
 
the effect of treating the child with SPN-8 the Parenting Stress Index – Short Form (
 
the effect of SPN-810 on the Caregiver-ra
 
the effect of SPN-810 on inattention and Rating Scale
 
the effect of SPN-810 on the responder ra frequency of IA behaviors)
 
	-rated Clinical Global Impression – Improvement all health as measured by the Child Health Q-PF28) 810 on the parent-child relationship as measured by PSI-4-SF)
Tertiary Study Design: Double-blind, placebo-controlled, Based on the 810P301 study Interim Analysis resu	

Based on the 810P301 study Interim Analysis result decision, the 18 mg dose arm was dropped partway through the study. As a result, subjects in the 18 mg dose arm will be re-randomized in a ratio of 2:1 to receive SPN-810 36 mg/day or placebo.

**Number of Subjects:** Approximately 398 subjects aged 6-12 years (inclusive) will be screened to achieve 306 subjects randomized.

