# 6.10 Sample Size and Power Considerations

Based on results from the Phase 2 study, a 15-point average difference in favor of the SPN-810 treatment arms compared with placebo is assumed; the change from baseline to endpoint in total R-MOAS rating was used to evaluate the difference. The R-MOAS was used because there have been no prior studies with the IA diary. A common standard deviation of 34.83 was obtained from a blinded analysis of SPN-810P301 data.

Based on these parameter assumptions, a sample size of approximately 122 per arm will yield 90% power to detect a non-zero difference between the median of SPN-810 treatment and the placebo groups using the Wilcoxon rank-sum test with a 2-sided significance level  $\alpha$ =0.05.

The original sample size of 291 was based on having 3 treatment groups (97 subjects per arm) and specific assumptions on the drug placebo difference, standard deviation and discontinuation rate.

CONFIDENTIAL Version 7.0

[figure not shown]
After the 810P301 study Interim Analysis result was completed, the 18 mg dose arm was discontinued and subjects planned to be randomized to the 18 mg arm would be re-allocated to the 36 mg or placebo arm in a ratio of 2:1. As such there will be an unequal randomization between the 36 mg dose group and placebo. With this post-interim analysis un-equal randomization, the placebo arm is expected to approach approximately 121 subjects of the total of 306 subjects randomized.

The sample size was calculated using the nQuery Advisor Software, Version 7.

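### 306 is the requirement for two arms, but SAP 3.5 fills part of it with 18 mg subjects who are never tested, so most of the 20% attrition allowance is already spent; the allocation statements also imply different placebo counts

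*SAP*

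**What the plan says.** Protocol 6.10 assumes a difference of 15 and an SD of 34.83, and says that "a sample size of approximately 122 per arm will yield 90% power to detect a non-zero difference". The test is the Wilcoxon rank-sum, two-sided at 0.05.

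SAP 3.5 carries this to the total: "This new SD leads to a total sample size of 306 (adjusted for 20% attrition) subjects". It continues: "Approximately 167 subjects were randomized prior to the implementation of the 2:1 randomization", and "It follows that 139 subjects would be randomized in a 2:1 ratio of 36 mg" (the comparator is missing from that sentence). So 167 + 139 = 306.

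Allocation after the change is described in several ways:

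- SAP 3.3.3, with Protocol 3.2.2.1, 4.3.4 and 6.10, applies 2:1 only to the slots intended for 18 mg: "subjects planned to be randomized to the 18 mg arm will be re-allocated to the 36 mg or placebo arm". SAP 3.5 also says this in an earlier sentence: "Subjects planned to be randomized to the 18 mg arm were re-randomized to the 36 mg or placebo arms at a 2:1 allocation ratio".
- The last allocation sentence of SAP 3.5, read as written, puts all 139 at 2:1.
- The protocol synopsis, under study design, speaks of people already on the arm: "subjects in the 18 mg dose arm will be re-randomized in a ratio of 2:1".
- Protocol 6.10 gives one resulting count: "the placebo arm is expected to approach approximately 121 subjects of the total of 306 subjects randomized".

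SAP 6.1 keeps 18 mg in the tabulations and limits testing to 36 mg and placebo. SAP 7.2 confirms that 18 mg receives summary statistics only.

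**The concern.** A total derived for two arms is being filled with subjects from three. Every subject already on 18 mg takes a place in the 306 and contributes nothing to the primary comparison, so the attrition margin that SAP 3.5 claims is largely used before anyone drops out. The allocation sentences also cannot all describe the same scheme. A reader cannot recover the planned sizes of the two tested arms or tell which sizes the stated 90% refers to. In a confirmatory trial, that matters for interpreting a negative or borderline result.

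**Working it through.** **Inputs.** Difference 15, SD 34.83, 122 per arm for 90% power (Protocol 6.10); 20% attrition, about 167 randomised before the change and 139 after (SAP 3.5); 1:1:1 before the change (SAP 3.3.3); 18 mg untested (SAP 6.1, 7.2). The number on 18 mg is not stated. It is inferred here from exact 1:1:1.

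**1. Reproduce the plan's figures.** Noether's formula for the rank-sum test: p = Φ(15 / (34.83 × √2)) = 0.6196, and n per arm = (1.96 + 1.2816)² / (6 × (p − 0.5)²) = 122.4, against the stated 122. The same formula with the original SD of 27.3 gives 76.6, i.e. the original 77, so the method matches the sponsor's. Then 122 / 0.8 = 152.5, rounded up to 153, and 2 × 153 = 306. Three arms would need 3 × 153 = 459. So 306 is a two-arm number.

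**2. What the 306 contains.** 167 / 3 = 55.7 on 18 mg. Tested arms: 306 − 55.7 = 250.3. Evaluable needed: 2 × 122 = 244. Intended allowance: 306 − 244 = 62; remaining: 250.3 − 244 = 6.3. That covers 1 − 244/250.3 = 2.5% loss, not 20%.

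**3. Placebo count under each statement.**

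- All 139 at 2:1: 55.7 + 139/3 = 102.0 (36 mg: 148.3).
- Only 18 mg slots at 2:1: the placebo share is 1/3 + 1/9 = 4/9, so 55.7 + 139 × 4/9 = 117.4 (36 mg: 132.9).
- Protocol: about 121.

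Two routes lead to 121. Under the slot rule, x/3 + (306 − x) × 4/9 = 121 gives x = 135 prior subjects, hence 45 on 18 mg, arms of 140 and 121, and 261 tested; the allowance is then 261 − 244 = 17. No document gives 135. Alternatively, if existing 18 mg subjects are themselves split 2:1 and all 139 also go 2:1, placebo is 167 × 4/9 + 139/3 = 120.6 and 36 mg is 167 × 5/9 + 139 × 2/3 = 185.4. That puts all 306 in the tested arms and leaves no 18 mg group.

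**4. Power for the tested arms.** Power = Φ(√(12·c(1−c)·N) × (p − 0.5) − 1.96), where N is the evaluable total and c the placebo share. Slot rule at 20% loss: N = 0.8 × 250.3 = 200.3, c = 0.469, giving 0.833. Each range below spans three approximations: Noether, a z-test scaled by 3/π, and simulation with normal data (40,000 runs).

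| Arms (36 mg / placebo) | 20% non-evaluable | 5% non-evaluable |
|---|---|---|
| 133 / 117 (slot rule, 167 prior) | 83–84% | 89–90% |
| 148 / 102 (139 at 2:1, 167 prior) | 82–83% | 88–89% |
| 140 / 121 (slot rule, 135 prior) | 85–86% | 90–91% |
| 185 / 121 (all 306 tested) | 89–90% | 93–94% |
| 153 / 153 (as 306 was derived) | 90–91% | 94–95% |

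With no loss, the first three rows give about 90–92%. None of these figures includes the mITT exclusion of subjects with baseline IA frequency below 6 per week.

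**The case against.** The case on the other side has four parts.

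**Real loss is probably below 20%.** Under SAP 7.1.3, ITT membership needs one dose and one valid post-randomisation diary assessment, and the endpoint uses whatever diary days exist (SAP 6.4). Most dropouts therefore stay in the rank test, and at 5% loss power is 88–91%. This stands and limits the practical damage. It does not rescue the statement that 306 carries a 20% adjustment, and the plan gives no expected evaluability to put in its place. The primary mITT population also removes subjects for whom 306 makes no stated allowance.

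**Only 121 is printed.** The 102 and 117 are derived, the 102 from a sentence with its comparator missing that may be shorthand for the slot rule. The gap between 117 and 121 is small and both inputs are approximate. That is fair: 117 against 121 alone would be weak evidence of two rules. The sentence with the 139 still needs correcting, because read as written it gives a placebo arm 15 to 19 subjects smaller.

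**The 18 mg count is inferred.** True. The 45, the 261 and the 85–86% depend on a hypothetical 135 prior subjects and err in the sponsor's favour. On the documented 167, power at 20% loss is 82–84%.

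**Perhaps existing 18 mg subjects were re-randomised.** The synopsis wording, and similar wording in Protocol 3.2.3, permit this, and 120.6 matches 121 closely. The lost allowance would then disappear. However, SAP 6.1 and 7.2 retain an 18 mg group to summarise, and the other allocation passages refer to subjects who had only been planned for that arm. If this reading is meant, those passages need correcting instead.

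**Conclusion.** The concern holds. The 306 reproduces exactly as a two-arm requirement, and SAP 3.5 counts untested 18 mg subjects toward it. With an 18 mg group retained, as the SAP says, about 250 to 261 subjects are in the tested comparison and only about 6 to 17 of the 62-subject allowance remain. Power at the plan's own 20% loss is about 82–86% rather than 90% (82–84% on the documented 167), and about 88–91% at 5% loss. These figures assume exact 1:1:1 allocation before the change and an 18 mg count that no document states. The shortfall may be small in practice. The stated margin is nevertheless not delivered by the design as described, and the allocation statements conflict.

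**What to change.** In SAP 3.5 and Protocol 6.10, state the actual or expected numbers on 36 mg, placebo and 18 mg under a single allocation rule, taken from the randomisation records. Bring three statements into line with that rule: the protocol's 121, the SAP sentence placing 139 subjects at 2:1, and the synopsis wording about re-randomising subjects in the 18 mg arm. Then restate power for 36 mg versus placebo from those counts, at 20% non-evaluable (about 82–86% on the inferred counts) and at the evaluability actually expected (about 88–91% at 5% loss). Say that these figures leave out the mITT exclusion.

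The cost is a text change and a less favourable stated power at 20% loss. No additional patients are needed, and the test, alpha and decision rule are unchanged.
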